#### Cost Analysis

A cost-utility analysis will be conducted. This will be cost per trainee in each group.

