# **Executive Summary**

The leading cause of blindness in China and the world more generally is un-operated cataract. Despite notable efforts on the part of the Chinese government, China's cataract surgical rate (1400/million/year in 2015) remains lower than that of many of its poorer neighbours, such as India (6500) and Vietnam (2250). An important reason is the unavailability of trained surgeons. Although China has over 36,000 ophthalmologists, only a third are capable of performing independent cataract surgery. This shortfall is due in large part to a lack of hands-on training opportunities. For instance, a recent survey of residents at China's top-ranked resident training programs found that the median number of independent cataract surgeries performed was actually zero. The problem persists after formal training is completed and looks set to worsen as experienced surgeons retire: in recent years, <5% of cataract surgeries were performed by doctors aged 24-43 years. The problem is particularly acute in rural areas, where hands-on training opportunities for young ophthalmic surgeons are even rarer. One reason is safety concerns on the part of patients and senior doctors in entrusting operations to young surgeons.

New training models for cataract surgery are needed which can safely and efficiently support trainees during the transition from novice to competent surgeon. Simulation-based surgical training, using high-fidelity, inexpensive, re-usable model eyes have been successfully piloted. We now propose to study these in a randomized trial comparing a programme that combines training using these model eyes and training using traditional techniques versus traditional training alone, to assess the impact on quality of surgery (assessed by masked grading of videos using the ICO OSCAR system), visual acuity and cost-utility outcomes. We hypothesize that the hands-on training with the model eyes will be a valuable addition to the more didactic standard training.

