#### Secondary outcomes:

- Mean presenting logMAR visual acuity on post-operative day (POD) 1 of ten successive cases with patient consent per surgeon (measured using the BOOST [Better Operative Outcome Software Tool] application.
- Mean improvement in lines of visual acuity in operative eye at POD 1.
- Cost per trainee in each group.

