#### **China-OLIMPICS Trial Intervention Objectives and Timetable**

#### Follow-up

### Participant Follow-up schedule:

Data collected at follow-up in the County Hospital:

• Surgical recording of ten live SICS procedures (supervised by the trainer).

### Patient Follow-up schedule: Post-op Day 1

Data at follow-up:

- Uncorrected and best-corrected visual acuity in operative eye (post-operative day (POD) 1)
- Ocular examination of operative eye with dilation of pupil to detect any co-morbidity undetected at baseline examination (POD 1)

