Queen's University Belfast: [name] is the Director of Translational Research for Equitable Eyecare (TREE) at QUB, a leading global eye health research centre. This centre includes six senior researchers in eye health, and a staff of statisticians, health economists and program managers fluent in Chinese to support projects in China such as the proposed research. QUB will offer the time of [name], statistician [name] and health economist [name] in kind to the project. [name] will oversee the randomization, drafting of study forms and protocols and statistical analysis in the project. [name] will oversee the health economic analyses (training costs and cost per line of vision gained per patient).

International Centre for Eye Health (London School of Hygiene and Tropical Medicine): ICEH is a global leader in research and training for the delivery of high-quality eyecare in low-resource areas. Collaborators [name] and [name] have developed and refined a bespoke training course around low-cost, re-usable, high-fidelity model eyes, which will be the focus of the current research. Their course will have incorporated use of the Orbis CyberSight platform prior to beginning the project in China. [name] will travel to China to supervise translation of the model eye training protocol to a Chinese setting, and provide oversight to the Chinese teams on maintaining quality throughout the training process.

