# Appendix 2 Budget

		Budgeted Spend (USD)				
	Itemised Costs of	6	12	18	24	
Budget Category	specific project	month	month	month	month	
	activities	s*	s*	s*	s*	TOTAL
		Target	Target	Target	Target	Target
		 	 	0	0	0
PERSONNEL (salaries,						
per diems, honoraria,						
etc.)						
	Orbis CyberSight					
	development of grading	C 000				C 000
	platform	6,000				6,000
	Patient baseline					
	questionnaire					
	collection: \$10/patient					
	* 280 patients	400	1,200	1,200		2,800
	Local post doctoral					
	research coordinator					
	the full period of					
	project					
	implementation)					
	\$875/mo					
	(CNY6000/mo) * 18					
	months	1,750	5,250	5,250	3,500	15,750
	Data sellestion on					
	visual acuity outcomes:					
	\$10/case X 280 cases	400	1.200	1.200		2.800
	+					
	Top-up fees for surgerv:					
	\$20/case*280 cases	800	2,400	2,400		5,600
	Grading of 280 +56					
	videos by senior					
	cataract surgeons at					
	\$10/video	960	1,200	1,200		3,360
	Patient endline					
	questionnaire					
	collection: \$10/patient					
	* 280 patients	400	1,200	1,200		2,800

	Data entry for forms: 4 forms/patient*280 patients*\$3/form				3,360	3,360
	Data analysis (Also includes support for form creation, creation of database and randomization process): Statistician \$1300/mo (CNY9,000/mo) * 100%time * 6 months	3,500	800		3,500	7,800
Personnel Sub-total		14,210	13,250	12,450	10,360	50,270
EQUIPMENT (including consumables, rentals, etc.						
	Model eyes (14 surgeons*8 eyes/surgeon*\$60/ eye) Phillips	6,720				6,720
	Mannequins and mounts for model eyes Phillips	2,400				2,400
	Kitaro DryLab artifical eye system	2,200				2,200
	Zeiss Stemi 305 ECU microscopes for training on artifical eyes (4 * @ \$2,000)	8,000				8,000
	Video cameras \$800*5 cameras	4,000				4,000
	Laptop@ \$800	800				800
Equipment Sub-total		24,120	0	0	0	24,120
TRAVEL						

	Travel to China for investigator [name]: \$1500 return fare, \$150 hotel/night and \$50/day food X 10 days	3,500				3,500
	Patients transport: 280 patient*\$15 each	600	1,800	1,800		4,200
	Travel to China for investigator [name]: \$1500 return fare, \$150 hotel/night and \$50/day food X 5 days			2,500		2,500
Travel Sub-total		4,100	1,800	4,300	0	10,200
TOTAL PROGRAM COSTS		42,430	15,050	16,750	10,360	84,590
FACILITIES & ADMINISTRATIVE	Indirect Costs	2,375	2,375	2,375	2,375	9,500
TOTALS		44,805	17,42 5	19,12 5	12,73 5	94,090

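### The analysis labelled cost-utility is defined as cost per trainee, with no utility or effect in it, and the planned cost per line of vision gained never reaches the outcomes or analysis sections

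*Combined protocol and SAP*

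**What the plan says.** The Executive Summary says the trial will assess the effect of the training on quality of surgery and on "visual acuity and cost-utility outcomes". Under Secondary outcomes, the only economic entry is "Cost per trainee in each group". The Cost Analysis section consists of two sentences: "A cost-utility analysis will be conducted. This will be cost per trainee in each group".

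A different measure appears under Department resources, collaborators & contractual arrangements. There the health economist at Queen's University Belfast is to oversee analyses of "training costs and cost per line of vision gained per patient".

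Lines gained is itself a listed secondary outcome, "Mean improvement in lines of visual acuity in operative eye at POD 1", and Statistical Analysis compares it between the arms.

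Baseline data and the patient follow-up schedule list acuity and ocular examination, with no utility or quality-of-life measure. The VFQ appears only in the glossary. Appendix 2 Budget pays for baseline and endline patient questionnaires but does not name the instrument.

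**The concern.** A cost-utility analysis relates cost to a utility measure. The second sentence of Cost Analysis replaces that with cost alone, so it contradicts the first. A statistician working from the outcomes and analysis sections would produce two average costs and nothing that relates them to benefit.

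Those two averages are not very informative. The Intervention section describes about 16 hours of simulation training that enhances the STEER course and replaces none of its content. A higher cost in the intervention arm is therefore the expected result whether or not the training works. The protocol says elsewhere that it wants to support scale-up and influence investment in training units. Readers with that interest need to know what the extra cost buys. If a bare cost difference is published under a cost-utility label, it will be taken for an answer it does not contain.

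**Working it through.** **1. What each place commits to**

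| Place | Economic measure | Effect in it? |
|---|---|---|
| Executive Summary | cost-utility outcomes | implied, not defined |
| Objectives | none | – |
| Secondary outcomes | cost per trainee | no |
| Cost Analysis | cost-utility, defined as cost per trainee | no |
| Department resources (Queen's University Belfast) | training costs; cost per line gained per patient | yes, lines of vision |

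These are three different endpoints. Only cost per trainee stands in the sections that govern the analysis. The Queen's University Belfast wording also leaves open whether the ratio is an average within each arm or an incremental ratio between arms.

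**2. Size of the foreseeable cost difference**

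The plan states no cost per trainee, so there is no such figure to reproduce. The budget lines are the only inputs (Appendix 2 Budget).

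- Model eyes: 14 × 8 × $60 = $6,720, which matches the budget. Per trainee: 6,720 / 14 = $480.
- Reusable items: mannequins and mounts $2,400, Kitaro system $2,200, microscopes $8,000. Sum: $12,600.
- All four lines: 6,720 + 12,600 = $19,320. Over 14 trainees: 19,320 / 14 = $1,380.
- With 17 trainees per arm (half of the 34 selected): eyes 17 × 8 × $60 = $8,160; (8,160 + 12,600) / 17 = $1,221.

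The range of $480 to $1,380 reflects how reusable equipment is charged. It excludes trainer time and the Training-the-Trainers course, for which the protocol gives no cost.

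**3. What the missing ratio would look like (illustration only)**

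The protocol gives no expected gain in lines, so the gains below are assumed. With 10 study patients per surgeon:

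incremental cost per line per patient = incremental cost per trainee / (10 × extra lines gained)

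| Extra lines (assumed) | at $480 | at $1,380 |
|---|---|---|
| 0.25 | $192 | $552 |
| 0.5 | $96 | $276 |
| 1 | $48 | $138 |
| 2 | $24 | $69 |

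The number of patients matters as much as the costing rule. If the cost were spread over the STEER minimum of 30 assisted plus 50 supervised cases (80), and the gain were assumed to persist over all of them, one extra line at $1,380 would cost 1,380 / 80 = $17.25 instead of $138. The plan must therefore state the denominator.

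**The case against.** The strongest reply is that an effect-based economic analysis is planned. The Queen's University Belfast paragraph names it and assigns it to a health economist, and its denominator is a secondary outcome compared between arms. This stands against a stronger reading that a reader might draw from Cost Analysis alone, namely that the trial's only economic result will be a price difference. The documents do not support that reading. What is missing is the transfer of the measure into Secondary outcomes and Cost Analysis.

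Three further objections also stand:

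- **Economic aim.** The Objectives name surgical competence and visual acuity and no economic question. The cost-utility aim rests on the Executive Summary phrase and on Cost Analysis itself.
- **Direction of the cost difference.** A reader might infer that the intervention arm must cost more. STEER is specified by a 2–4 week range and by minimum numbers of pig eyes and cases, so use of standard training could differ between arms and offset some cost. A higher cost is expected, not fixed. However, no collection of resource use is described that would detect an offset.
- **The $1,380.** This is one costing choice, not an estimate of incremental cost, because it charges all reusable equipment to 14 trainees and omits trainer time.

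The budgeted questionnaires and the glossary entry for the VFQ might point to an intended utility measure. They do not establish one, since no section names the instrument or its timing, but they do leave a second route to a repair.

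**Conclusion.** The economic plan is wrong as written. Cost Analysis attaches a cost-utility label to a quantity with no utility, effect or incremental comparison, and it cannot deliver what the Executive Summary announces. The measure that could inform value sits in a description of staffing resources and is absent from the outcomes and analysis sections. This rests on the wording of those sections alone.

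The expected cost difference, about $480 to $1,380 per intervention trainee from budgeted items, depends on the charging rule and on planned rather than actual spending. The cost-per-line figures depend on assumed gains and show scale only.

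The consequence is moderate. This is one secondary outcome, and the co-primary OSCAR comparisons, the sample size and the randomisation are untouched. The change should be made because it is cheap and the effect data are already planned.

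**What to change.** 1. In the Executive Summary and Cost Analysis, replace the cost-utility label with cost-effectiveness. Keep cost per trainee by arm as a descriptive input.
2. Add to Secondary outcomes and Cost Analysis the incremental cost per additional line of vision gained per patient. Define it as the difference in training cost per trainee, spread over a stated number of patients per surgeon (10 in the study), set against the difference in mean lines gained at POD 1.
3. Report joint cost and effect uncertainty on a cost-effectiveness plane, or as net benefit over a range of values per line. A confidence interval for the ratio alone is unstable if the effect difference is near zero. Use a bootstrap that resamples surgeons as clusters and respects the 10 randomisation strata as far as their size allows. Some strata are hospitals with two participants, so resampling within arm and stratum may leave a single surgeon to draw from.
4. Show reusable equipment both fully charged to the trial and spread over its use.
5. State the perspective and list the cost items, including trainer time, and record them. Baseline data and follow-up list no cost or resource-use data at present.
6. A cost per OSCAR point is optional. If given, show it for both co-primary scores.

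Alternatively, if the budgeted baseline and endline questionnaires are a utility measure, name the instrument, its timing and its analysis, and keep the cost-utility label.

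The cost is a wording amendment, a short cost-recording form and some time from the health economist already assigned. No new patient data are needed for the first route.

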### **Prevention of Bias**

It is accepted that there will be variability in individual participants' inherent or natural surgical aptitude. In order to attempt to reduce the effects of this, the two groups will be balanced with regard to the baseline OSCAR scores of participants, and their total number of previous surgical cases. This however will only occur in final analysis, and not before randomisation or training.

All efforts will be made to standardise the training offered to the 'Intervention' participants. The intense simulation course will be held in the same Training Centres. The training will be conducted by experienced trainers who have undertaken a specifically designed 'Training the Trainers' course. All recordings of surgical procedures will be performed using the same recording system.

Video recordings of procedures will be allocated a random 7-digit number, and subsequently stored onto an encrypted computer, and a separate encrypted hard drive. This random number will be the only identifiable information available when the simulation/surgical procedure is assessed, thus masking the assessor to the participant's randomised group.

It is recognised that surgical education is complex and multi-faceted. However, every effort will be made to reduce 'contamination' bias. Participants will sign an informed consent form detailing that they will in no way share any of the details of the course or educational intervention with any surgeon who is not known to be in the same randomised group as themselves; for a minimum of six months following the end of the training programme in Tongren.

The PIs and co-investigators declare that they have no financial or other conflicts of interest that are relevant to this randomised trial.

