# Methodology

Study Design: Randomized controlled trial of an educational intervention.

Study Population: Cataract surgical trainees learning to perform small-incision cataract surgery (SICS) in the Orbis/Chinese Ophthalmic Society Rural Training Program (STEER). (This is a currently funded Orbis project, thus reducing the costs for this randomised trial.)

Partners: Orbis International and Queen's University Belfast ([name] is affiliated with both); Tongren Hospital and the Chinese National Committee for the Prevention of Blindness ([name] heads both); and International Centre for Eye Health at the London School of Hygiene & Tropical Medicine ([name], [name])

Sample Size Calculations: Based on OSCAR (ophthalmology surgical competency assessment rubric) scores for different surgical steps among SICS trainees at Aravind, India: 14 doctors in each of two groups operating on 10 patients each (total 280 surgeries) would allow for detection of a difference in mean OSCAR scores (across all steps) of 1.0 (point per set) between groups with a power of 0.9, alpha-error of 0.05, a standard deviation of 1.0 for scores, and an ICC of 0.57 for scores across cases within surgeon. The ICC value comes from our review of SICS cataract surgical training assessed using OSCAR in other Orbis training programs. (As this main outcome will be captured during surgery, there is no need to inflate our required sample size estimate to allow for loss to follow-up).

A total of 34 participants has been selected, to allow for a 15% attrition rate.

ICO-OSCAR scores cover 19 categories, with each category score ranging 0 to 5, and therefore with an overall 0 to 95. An example of a 1.0 point difference within the category, "Conjunctival and Corneal Tissue Handling" is for a Competent score (score = 5) the "tissue is not damaged nor at risk by handling," while for an Advanced Beginner score (score = 4), "tissue handling decent but potential for damage exists."

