### Patient Exclusion Criteria:

- Fellow eye has an irreversible cause of visual impairment
- Any prior ophthalmic surgery in the proposed operative eye
- Any co-morbid condition in the operative eye likely to impact post-operative visual acuity negatively (conditions only detected on post-operative examination would also lead to retrospective exclusion)

Intervention: Standard surgical training (as described below for "Control") plus a new, bespoke simulation-based training scheme using low cost, reusable model eyes combined with practical surgical exercises, developed in Africa by ICEH collaborator [name]. *See page 17*.

**Control**: Standard surgical training (without the bespoke training scheme that uses simulation and model eyes) in the ORBIS-COS administrated STEER project, mentioned above. Trainees complete 2-4 weeks of didactic lectures, surgical observation, and wet-lab training at a provincial training centre with a minimum of 50 pig eye wet-lab simulations per trainee. After observed mastery of wet-lab pig eyes, trainees then perform hands-on training in County level hospitals. The hands-on training pairs a surgeon from the training centre who travels to the county level hospital to mentor the trainee through a minimum of 30 assisted surgeries, and 50 'independent' surgeries under supervision. This project and its cataract surgical training protocol have been approved by the Chinese National Blindness Prevention Committee, who are essential partners.

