#### Randomisation (stratified blocked randomization):

Participants who have reached the appropriate inclusion and exclusion criteria for the trial will be eligible for randomisation to 'intervention' or 'control'.

Eligible trainees completing baseline data collection will be enrolled into the study and stratified into 10 groups\* according to their training center and hospitals (home facilities). The hospitals with only one participant are combined to form a mixed group. Participants in each of the 10 stratified groups will be assigned at random to one of the study arms as shown in the following figure.

An independent statistician having no contact with participants will generate the randomization sequences (lists) using a computer system that is inaccessible until after recruitment. The random sequence includes three types: (1) A list of the mixed hospitals with only one participant; (2) A number of lists of the hospital with paired participants (3) Individual list(s) of the hospitals with more than two participants. Each random sequence comprises of sequence numbers and their corresponding codes (e.g. two letters plus a 4-digit number). Codes are used to represent the Intervention or Control group; a codebook is created for decoding the group allocations.

To preserve allocation concealment, a two-step procedure will be used for random allocation in each training center.

**Step 1**: Project manager (PM) sends randomization sequences to the Quality Control officer (QCO). QCO assigns a code to each participant from the randomization sequences. QCO update the random lists with participant's names and send it to PM. At the end of this step, neither the QCO or participants know what group the codes refer to.

**Step 2:** As soon as receiving result file from QCO, PM checks the codebook, update the file with participant's names and send it back to QCO. QCO allocates the participants into control and intervention groups and completes the random allocation.

The participants will know their group assignment. However, the staff(s) grading video recordings of assessments will be masked by having a randomized number assigned to each video.

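### The six-month undertaking not to share course details is not tied to the end of outcome recording, so early-trained intervention surgeons could be released while control colleagues' cases are still to be recorded

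*Combined protocol and SAP*

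**What the plan says.** Under Prevention of Bias, participants sign that "they will in no way share any of the details of the course or educational intervention with any surgeon" outside their own randomised group. The term is "for a minimum of six months following the end of the training programme in Tongren".

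Four other places bear on whether that term is long enough:

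- **Randomisation.** Allocation is stratified by training centre and home hospital. The lists include "A number of lists of the hospital with paired participants", lists for hospitals with more than two participants, and one list pooling hospitals with a single participant. Participants know their arm.
- **Control paragraph (after Patient Exclusion Criteria).** Trainees have lectures, observation and "wet-lab training at a provincial training centre", then do hands-on cases in county hospitals.
- **Appendix 2 Budget.** Per-case costs, such as the surgery top-up of $"20/case*280 cases", are spread over the 6-, 12- and 18-month columns, with nothing in the 24-month column.
- **Surgeon Exclusion Criteria.** A surgeon who is not willing to talk about surgical training with a colleague in the other arm is excluded. As worded, this pulls against the undertaking.

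**The concern.** The comparison is protected only if control surgeons remain unexposed until their ten outcome cases are on video. A fixed term counted from the end of training does not ensure that. What matters is not only whether a surgeon's own ten cases fall inside that surgeon's own six months. An intervention surgeon whose term has ended may also work alongside a control surgeon whose cases have not yet been recorded, and within-hospital randomisation creates such pairs.

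Some of the course could be passed on informally: how the operation is broken into stages, repeated practice on apples and tomatoes, and the videos. Any benefit that reached controls this way would shrink the arm difference. In a superiority trial that favours a false conclusion that the model-eye course adds little, and the exposure cannot be undone later.

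The starting point of the term is also unclear. A participant trained at a provincial centre cannot tell from a clause about Tongren when the six months begin.

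**Working it through.** **1. The plan's own case count.** Methodology gives "14 doctors in each of two groups operating on 10 patients each (total 280 surgeries"), for a difference of 1.0, SD 1.0, ICC 0.57, alpha 0.05 (taken as two-sided) and power 0.9.

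- Independent cases per arm: 2 × (1.960 + 1.282)² × 1.0² / 1.0² = 21.01, rounded up to 22.
- Design effect: 1 + (10 − 1) × 0.57 = 6.13.
- Surgeons per arm: 22 × 6.13 / 10 = 13.49, so 14. Then 2 × 14 × 10 = 280 cases.

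The 280 is reproduced.

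**2. The calendar implied by Appendix 2 Budget.** Divide each column by its unit cost.

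| Line | Unit cost | 6 months | 12 months | 18 months | Sum |
|---|---|---|---|---|---|
| Surgery top-up | $20 | 800/20 = 40 | 2,400/20 = 120 | 2,400/20 = 120 | 280 |
| Visual acuity collection | $10 | 400/10 = 40 | 1,200/10 = 120 | 1,200/10 = 120 | 280 |
| Patient transport | $15 | 600/15 = 40 | 1,800/15 = 120 | 1,800/15 = 120 | 280 |

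The columns add up to the line totals, so they are amounts per period, not cumulative. On this calendar, outcome cases run to month 18 and 120/280 = 42.9% fall in months 13 to 18.

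**3. Share outstanding when the minimum term expires.** Let T be the month in which training ends. The readable text does not give T, so it is varied here. As a simplification, one T applies to everyone and cases are spread evenly within each column. With C(t) the cumulative cases by month t, the share is 1 − C(T + 6)/280.

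| T | Expiry (month) | C(T + 6) | Share outstanding |
|---|---|---|---|
| 0 | 6 | 40 | 240/280 = 86% |
| 3 | 9 | 100 | 180/280 = 64% |
| 4 | 10 | 120 | 160/280 = 57% |
| 6 | 12 | 160 | 120/280 = 43% |
| 9 | 15 | 220 | 60/280 = 21% |
| 12 | 18 | 280 | 0% |

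**4. If trainees come in waves.** Hands-on cases follow centre training, so whoever supplies the 40 cases in the first column has finished the centre phase by month 6. At ten cases each, that is 40/10 = 4 surgeons if they complete their sets, or more surgeons with part-sets. Counted from the end of the centre phase, their minimum term can expire by month 12, with up to 120 cases still to come. Surgeons who finish in months 7 to 12 stay bound until months 13 to 18.

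**5. Illustration only: what transfer would do.** Suppose that all training ends at month 6, that every control case after month 12 is exposed, and that exposure passes on 25% to 50% of the benefit. None of these three assumptions comes from the documents.

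- Arm difference: 1 − 0.429 × 0.25 = 0.89, or 1 − 0.429 × 0.50 = 0.79.
- Standard error under the plan's inputs: √(2 × 6.13 / (10 × 14)) = 0.296.
- Normal-approximation power: 0.92 at a difference of 1.0, about 0.85 at 0.89 and about 0.76 at 0.79.

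**The case against.** **The budget may not be a surgery schedule.** Coordinator pay at $875 a month works out at 2, 6, 6 and 4 months across the columns. The 40/120/120 cases are 20 a month over the same 2, 6 and 6 months, which looks like straight-line costing. The columns show study-wide spending, not any surgeon's time since training, and the Gantt chart that might settle this is not shown. This stands, and it is why a range is given. It does not show that recording ends within six months of training.

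**The undertaking may outlast a surgeon's own cases.** The Intervention section lists the assisted and supervised operations as part of the STEER course, and Outcomes takes the first 10 of 30 supervised cases. If the training programme means the whole course, a surgeon's own ten cases come before the six months even start. The text permits that reading, although a clause about Tongren fits the centre phase better than operations in county hospitals. The risk from a released surgeon to a later-trained control colleague would remain, but nothing in the text shows that hospital colleagues train months apart.

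**A reader might infer that 43% of outcome cases will be unprotected and that power will fall to about 0.76 to 0.85.** The documents do not support this. The 43% needs all training to end at month 6. The power figures also treat every control case after month 12 as exposed, whereas the wave argument releases only early-trained surgeons, and the transfer fraction is invented. Much of the course is hands-on model-eye practice with feedback, about 16 hours in total, which conversation cannot replace. Nor is Simulation-OSSCAR something that would leak: both arms meet it at the baseline assessment.

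**Tongren may be loose wording for the joint programme.** That is possible. The mismatch with the provincial centres is then editorial, and it cannot be said that many trainees lack the start event.

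**The term is a minimum, and the consent form may be stricter.** A minimum allows a longer term but does not require one. The surgeon consent form is not in the text available here, so its wording is unchecked.

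**Conclusion.** The point holds as a cheap improvement. The undertaking ends on a clock unrelated to the event it should protect, and on the centre-training reading it can expire while control colleagues' cases are unrecorded. Any resulting bias is towards zero.

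Its size is not determined by the readable text. The 0% to 86% range rests on treating the budget columns as the recording calendar, on one training end date for everyone, and on the shortest permitted term. No loss of power should be attributed to the plan; the figures in step 5 only show the direction. How often opposite-arm colleagues share a hospital is also unknown, because some strata pool single-participant hospitals.

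**What to change.** In Prevention of Bias, and in the surgeon consent form if it has the same term:

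1. Run the undertaking until the last outcome case of the last trial participant has been recorded, as notified in writing by the project manager, and never less than six months from the end of the participant's own training.
2. Replace the reference to Tongren with the participant's own training centre, and say whether the end of training means the centre phase or includes the county-hospital operations.
3. Reconcile the clause with the surgeon exclusion criterion on discussing training with a colleague in the other arm. Lengthening the term alone leaves that conflict in place.

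The cost is a few lines of text and one closing notice to participants. The downside is that some surgeons are bound for longer. Sample size and analysis are unchanged.
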